## 8.2.1 Adverse Event Reporting Period

The study period during which all AEs and SAEs must be reported begins after initiation of study treatment and ends at study completion or study discontinuation/termination, whichever is earlier. Any condition present between consenting and time of treatment will be considered as baseline and not recorded as an AE. After this period, investigators should report only SAEs that are attributed to study treatment.

All AEs that are observed or reported prior to initiation of study treatment will be recorded as unrelated to treatment and those occurring after initiation of treatment will be recorded as treatment-emergent.

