#### 5.3 Subject Discontinuation and Withdrawal

Subjects may voluntarily withdraw from the study at any time. In the event of early withdrawal, the reason for withdrawal will be recorded on the appropriate CRF. Attempts to complete early termination exam as defined in 7.4 will be made. The Investigator has the right to discontinue a subject from the study for any medical reason that the investigator determines may jeopardize the subject's safety if he or she continues in the study, or for reasons of noncompliance (e.g., missed visits, use of other investigational drugs, etc.). Each site Investigator may enroll up to 3 additional subjects to each group to offset subjects that are withdrawn or terminated.

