#### 6.4 **Concomitant Medications and Rehabilitation**

Concomitant medications (any prescription and/or over-the-counter preparations) and therapies (nondrug or procedures) used by a subject while participating in this clinical trial will be optimized per AHA Guidelines and recorded at screening and until the end of the study or the end of a subject's participation in the study. Subjects may be administered beta-blockers, ACE inhibitors or angiotensin receptors blockers,

mineralocorticoid receptor antagonists, statin agents, or other medications, as tolerated. All other prescription and over-the-counter preparations approved by the patients' physician will be permitted.

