#### 7.4 Early Termination Visit

- Measure and record weight and vital signs
- 12-lead ECG
- Pulse Oximetry
- 24 hour Holter ECG monitoring or ACD assessment
- Record the composite of all-cause mortality admission for worsening HF and all-cause admissions, and concomitant medication use
- Physical and cardiac examination
- Clinical labs: serum chemistry including BUN & creatinine, CBC with diff, LFT's, total protein and albumin
- Serum/plasma stored for VEGF, FGF, NT-proBNP, troponin
- Blood sample for IgA, IgE, IgG, IgM and for Lymphocyte Proliferation Panel
- 6 minute walk test
- Kansas City Cardiomyopathy Questionnaire (KCCQ)
- New York Heart Association (NYHA) Classification
- Cardiac MRI, with delayed contrast enhancement
- Full 2D and Doppler transthoracic echocardiography with speckle-tracking

The same follow-up visits will be performed after the crossover phase.

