Changes in the severity of an AE will be documented to allow an assessment of the duration of the event at each level of intensity to be performed. Adverse events characterized as intermittent require documentation of onset and duration of each episode.

**Relationship to Study Products:** The clinician's assessment of an AE's relationship to investigational product is part of the documentation process, but it is not a factor in determining what is or is not reported in the study. If there is any doubt as to whether a clinical observation is an AE, the event will be reported. All AEs must have their relationship to investigational product assessed. In a clinical trial, the investigational product must always be suspect. To help assess, the following guidelines are used.

- Related There is a plausible temporal relationship between the onset of the AE and administration of the investigational product, and the AE cannot be readily explained by the subject's pre-existing clinical state, intercurrent illness, or concomitant therapies; and/or the AE follows a known pattern of response to the investigational product; and/or the AE abates or resolves upon discontinuation of the investigational product and, if applicable, reappears upon re-challenge.
- Not Related There is good evidence that the AE has an etiology other than the investigational product (e.g., pre-existing medical condition, underlying disease, intercurrent illness, or concomitant medication); and/or the AE has no plausible temporal relationship to administration of the investigational product (e.g., cancer diagnosed 2 days after treatment).

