## 8.2.2 Assessment of Adverse Events

Investigators will seek information on AEs and SAEs at each subject contact by specific questioning and, as appropriate, by examination. All AEs and SAEs, whether spontaneously reported by the subject or noted by authorized study personnel, will be recorded in the subject's medical record and on the appropriate AE or SAE CRF page.

Each recorded AE or SAE will be described by its duration (i.e., start and end dates), severity, regulatory seriousness criteria if applicable, suspected relationship to the investigational product, and actions taken.

Note: The investigator's assessment of causality for individual AE reports is part of the study documentation process. Regardless of the "Yes" or "No" causality assessment for individual AE reports, the sponsor will promptly evaluate all reported SAEs against cumulative product experience to identify and expeditiously communicate possible new safety findings to investigators and applicable regulatory authorities. Attribution of SAEs will be reviewed on an ongoing basis, and may be changed as additional clinical data emerge (e.g., reversibility of AE, new clinical findings in subject with AE, effects of retreatment, AEs in other subjects).

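### No active follow-up is planned after a dosed subject leaves, and the reporting cut-off in 8.2.1 is ambiguous, so the all-cause primary composite can miss unattributed events

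*Combined protocol and SAP*

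**What the plan says.** - **Reporting window.** Section 8.2.1 opens reporting of all AEs and SAEs when study treatment starts. The window "ends at study completion or study discontinuation/termination, whichever is earlier". The section then adds: "After this period, investigators should report only SAEs that are attributed to study treatment".
- **Endpoint.** The synopsis and section 4.2 list, under the primary safety endpoint, a composite of death from any cause, admission for any cause and need for co-intervention such as IV diuretics. It has no attribution test. The primary safety items are due at 30, 60 and 90 days after each infusion.
- **Safety set.** The synopsis (Statistical Methods) includes every randomized subject who received any part of a dose.
- **Leaving the study.** Section 5.3 allows voluntary withdrawal at any time. It also says: "The Investigator has the right to discontinue a subject from the study for any medical reason", where continuing may endanger the subject, and it allows discontinuation for noncompliance. For early withdrawal, the reason is recorded and "Attempts to complete early termination exam as defined in 7.4 will be made". That exam includes: "Record the composite of all-cause mortality admission for worsening HF and all-cause admissions".
- **Detection.** Section 8.2.2 says: "Investigators will seek information on AEs and SAEs at each subject contact by specific questioning". It also requires AEs and SAEs that subjects report spontaneously or that staff notice to be recorded.
- **Other cover.** Section 8.2.3 e requires deaths during the study to be reported whatever their cause. Section 8.4 follows AEs and SAEs that are already open.

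**The concern.** The composite counts events from any cause, and a dosed subject who leaves stays in the safety set. Yet after the single termination exam the plan schedules no visit, telephone call or records check for that subject. On one reading of 8.2.1, whether a later SAE is reported depends on whether someone attributes it to treatment.

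Safety is the primary objective. Events that are not collected can only lower the number counted, and analysis cannot recover them later. Section 9 replaces no missing data. Its counts of subjects with complete data would show that information is missing, but not what it was. Subjects taken out for a medical reason are plausibly at higher risk of a later event. With 10 subjects in a group, each event that is missed is 1/10, or 10 percentage points of that group's incidence if the subject stays in the denominator.

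**Working it through.** The plan states no figure to reproduce: section 9.4 says that the sample size does not rest on power, and no dropout rate is given. The check is a reading of the text, followed by an illustration of scale.

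**Step 1: whose discontinuation?**
- For the subject: the window opens at the subject's own treatment, 5.3 uses discontinuation for subjects, and the early termination visit in 7.4 is a subject's visit.
- For the trial: 5.4 (Study Termination) concerns the sponsor ending the trial, and 10.2 (Study Completion) concerns closing it.
- Section 6.4 shows that the authors could separate the two, since it records medications "until the end of the study or the end of a subject's participation in the study". Section 8.2.1 makes no such distinction, so the text does not settle the question.

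**Step 2: what is captured after a dosed subject leaves?**

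| Event | Subject-level reading | Trial-level reading, trial still running |
|---|---|---|
| Before exit, seen at a visit or the exit exam | Captured | Captured |
| AE or SAE already open at exit | Followed (8.4) | Followed (8.4) |
| New SAE attributed to treatment | Reportable | Reportable |
| New unattributed death | Outside the 8.2.1 rule | Reportable (8.2.3 e) |
| New unattributed admission | Outside the 8.2.1 rule | Reportable, but not actively sought |

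The last row is a gap in both columns. The death row is a gap only in the first.

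**Step 3: scale, as illustration only.** Take one 90-day infusion period with 10 infused subjects (the group size in 4.1 and 5.1; 5.2 and 6.1 also print 15). The remaining inputs are assumptions, none from the documents:
- true 90-day composite rate p of 10%, 20% or 30%, with constant hazard;
- exits spread evenly over the 90 days;
- leavers kept in the denominator and not replaced;
- no late event attributed to treatment or reported passively.

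With L = −ln(1 − p), the probability that a leaver's event falls after exit is q = p − (1 − p/L). For p = 20%, L = 0.2231 and q = 0.20 − (1 − 0.8963) = 0.0963. With k leavers, the share of events lost is kq/(10p), and the chance of losing at least one is 1 − (1 − q)^k.

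| | p = 10% | p = 20% | p = 30% |
|---|---|---|---|
| q | 0.0491 | 0.0963 | 0.1411 |
| Share lost, k = 1 | 4.9% | 4.8% | 4.7% |
| Share lost, k = 3 | 14.7% | 14.4% | 14.1% |
| Chance of losing at least one, k = 1 | 4.9% | 9.6% | 14.1% |
| Chance of losing at least one, k = 3 | 14.0% | 26.2% | 36.6% |

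At p = 20% the expected loss is 0.096 events with one exit and 3 × 0.0963 = 0.289 with three. A true 20% would be recorded as (2 − 0.096)/10 = 19.0% or (2 − 0.289)/10 = 17.1%.

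If leavers have rate 2p, q becomes 0.0963, 0.1830 and 0.2548, and total events are (10 − k)p + 2kp. The share lost is then 8.8%, 8.3% and 7.7% for one exit, and 22.2%, 21.1% and 19.6% for three.

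If three leavers at p = 20% are all replaced, so that 13 are infused, the share falls to 0.289/(13 × 0.20) = 0.289/2.6 = 11.1%.

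For a single case, a subject who leaves just after Day 30 loses 90 − 30 = 60 of the 90 days, and two of the three follow-up visits for that infusion.

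**The case against.** The strongest reply is that the cut-off in 8.2.1 may not touch leavers at all. Two of its three terms, completion and termination, match headings about the trial. On that reading nothing is cut off while the trial runs, and deaths are covered. This stands, so a reader should not infer that 8.2.1 certainly stops reporting when a subject leaves. Even on the subject-level reading, 8.2.3 e might be taken to reach a leaver who dies while the trial is open, which makes admissions the firmer gap.

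It is also tempting to say that late events have no route into the data. The documents do not support that. Section 8.2.2 records spontaneous reports, 8.1.1 expects AEs to surface when a subject presents for care or when a monitor reviews records, and 7.2.2 gives subjects a telephone number for changes in health. These routes are passive. What remains is that nobody is required to look.

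A reader might also see a contradiction with 8.1.1, which says of attribution that "it is not a factor in determining what is or is not reported in the study". That sentence concerns reporting within the study, whereas the limit in 8.2.1 applies after the reporting period, so the two can stand together.

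Three further points stand. Co-intervention is missing from the composite as listed in 7.1, 7.3 and 7.4 for every subject, so its loss is not peculiar to leavers. Section 9 analyses available data and nothing says that unobserved time counts as event-free, so a lower count need not mean a lower reported incidence. Section 5.3 allows up to 3 additional subjects per group at each site, which can dilute the loss. The trial is also exploratory and described as descriptive, which limits the consequence.

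None of this supplies active follow-up after exit.

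**Conclusion.** The point holds in a limited form. Section 8.2.1 leaves open whether its cut-off is the subject's or the trial's. On either reading, no active follow-up is planned after one attempted exit exam. New unattributed admissions, and on the subject-level reading unattributed deaths, can therefore be missed from an all-cause primary composite in subjects who remain in the safety set.

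The size is unknown and may be zero. The figures above are not estimates for this trial. They sit toward the high end for their assumed rates and numbers of exits, because they leave out attributed SAEs, passive reports and replacements. They also overstate what could be recovered, since some leavers will refuse further contact. A missed event would cost 10 percentage points in a group of 10, but with one exit the expected loss at p = 20% is about 0.1 event, or about 1 point.

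A reader might infer a bias toward or against the cells. The documents give no basis for a direction, and none is claimed. Severity is minor to moderate: a cheap improvement to a safety trial, not a flaw that undermines it.

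**What to change.** 1. In 5.3, separate discontinuing infusions or visits from withdrawing consent for follow-up. Only the second ends data collection.
2. In 8.2.1, state whether the end of the window refers to the subject or the trial. Add that, for every infused subject, all deaths, admissions (including those for co-intervention such as IV diuretics) and SAEs are collected regardless of attribution, by visit, telephone or records, through planned Day 180 unless consent for follow-up is withdrawn.
3. In the detailed analysis plan, which section 9 says is still to be written, tabulate events within 90 days of each infusion under that infusion. List later events in subjects who never received the second infusion separately, so that each treatment is counted over the same 90 days.

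The cost is wording in two sections, one tabulation rule, one consent line, and a few calls or record checks. Reported event rates may be slightly higher. Events in subjects who withdraw consent for follow-up would still go unobserved.

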## 8.2.2 Assessment of Adverse Events

Investigators will seek information on AEs and SAEs at each subject contact by specific questioning and, as appropriate, by examination. All AEs and SAEs, whether spontaneously reported by the subject or noted by authorized study personnel, will be recorded in the subject's medical record and on the appropriate AE or SAE CRF page.

Each recorded AE or SAE will be described by its duration (i.e., start and end dates), severity, regulatory seriousness criteria if applicable, suspected relationship to the investigational product, and actions taken.

Note: The investigator's assessment of causality for individual AE reports is part of the study documentation process. Regardless of the "Yes" or "No" causality assessment for individual AE reports, the sponsor will promptly evaluate all reported SAEs against cumulative product experience to identify and expeditiously communicate possible new safety findings to investigators and applicable regulatory authorities. Attribution of SAEs will be reviewed on an ongoing basis, and may be changed as additional clinical data emerge (e.g., reversibility of AE, new clinical findings in subject with AE, effects of retreatment, AEs in other subjects).

## 8.2.3 Recording Adverse Events on the CRF

Investigators will use correct medical terminology/concepts when recording AEs or SAEs on the CRF. Avoid colloquialisms and abbreviations.

AEs will be recorded either on an AE CRF page (if no serious criteria are met) or SAE CRF page, but not both. For each SAE observed, the investigator must report the triggering event for that particular episode of illness as the primary event.

Only one medical concept will be recorded in the event field on the AE or SAE CRF page.

## a. Diagnosis versus Signs and Symptoms

If known, a diagnosis will be recorded on the CRF rather than individual signs and symptoms (e.g., record only liver failure or hepatitis rather than jaundice, asterixis, and elevated transaminases). However, if a constellation of signs and/or symptoms cannot be medically characterized as a single diagnosis or syndrome at the time of reporting, each individual event will be recorded as an AE or SAE on the CRF. If a diagnosis is subsequently established, it will be reported as follow-up information.

## b. Adverse Events Occurring Secondary to Other Events

In general, AEs occurring secondary to other events (e.g., cascade events or clinical sequelae) will be identified by their primary cause. For example, if severe diarrhea is known to have resulted in dehydration, it is sufficient to record only diarrhea as an AE or SAE on the CRF.

However, medically significant AEs occurring secondary to an initiating event that are separated in time will be recorded as independent events on the CRF. For example, if a severe gastrointestinal hemorrhage leads to renal failure, both events will be recorded separately on the CRF.

#### c. Persistent or Recurrent Adverse Events

A persistent AE is one that extends continuously, without resolution between subject evaluation time points. Such events will only be recorded once in the CRF unless their severity increases. If a persistent AE becomes more severe, it will be recorded again on an AE or SAE CRF page.

A recurrent AE is one that occurs and resolves between subject evaluation time points and subsequently recurs. All recurrent AEs will be recorded on an AE or SAE CRF page.

#### d. Abnormal Laboratory Values

Laboratory data collection will be limited to those laboratory parameters that are relevant to safety, study outcome measures, and/or clinical outcome. Only clinically significant laboratory abnormalities that require active management will be recorded as AEs or SAEs on the CRF (e.g., abnormalities that require more frequent follow-up assessments, further diagnostic investigation, etc.) If the Investigator is uncertain about the appropriateness of reporting particular laboratory data, he/she will contact the Medical Monitor for the study.

If the clinically significant laboratory abnormality is a sign of a disease or syndrome (e.g., alkaline phosphatase and bilirubin five times the upper limit of normal associated with cholecystitis), only the diagnosis (e.g., cholecystitis) needs to be recorded on the AE or SAE CRF page.

If the clinically significant laboratory abnormality is not a sign of a disease or syndrome, the abnormality itself will be recorded as an AE or SAE on the CRF. If the laboratory abnormality can be characterized by a precise clinical term, the clinical term will be recorded as the AE or SAE. For example, an elevated serum potassium level of 7.0mEq/L will be recorded as "hyperkalemia."

Observations of the same clinically significant laboratory abnormality from visit to visit will not be repeatedly recorded as AEs or SAEs on the CRF, unless their severity, seriousness, or etiology changes.

#### e. Deaths

For any deaths that occur during the study, regardless of attribution, the investigator will report the death immediately to the Medical Monitor for the study at the telephone number provided on the cover of this protocol and record the death on the appropriate SAE CRF page.

When recording a death, the event or condition that caused or contributed to the fatal outcome will be recorded as the single medical concept on the SAE CRF page. If the cause of death is unknown and cannot be ascertained at the time of reporting, record "Unexplained Death" on the SAE CRF page.

#### f. Pre-existing Medical Conditions

A pre-existing medical condition is one that is present at the start of the study. This includes any abnormal physical examination finding noted during screening. Such conditions will be recorded on the Medical and Surgical History CRF page.

A pre-existing medical condition will be re-assessed throughout the trial and recorded as an AE or SAE only if the frequency, severity, or character of the condition worsens during the study. When recording such events on an AE or SAE CRF page, it is important to convey the concept that the pre-existing condition has changed by including applicable descriptors (e.g., "more frequent headaches").

## h. Hospitalization, Prolonged Hospitalization or Surgery

Any AE that results in hospitalization or prolonged hospitalization will be documented and reported as an SAE unless specifically instructed otherwise in this protocol. Any condition responsible for surgery will be documented as an AE if the condition meets the definition of an AE. Surgical procedures are not to be recorded as SAEs or AEs.

#### i. Pregnancy

If a female subject becomes pregnant during the study, a Pregnancy Report CRF page will be completed and expeditiously submitted to the sponsor to facilitate outcome follow-up. Pregnancy is not an SAE.

Abortion, whether accidental, therapeutic, or spontaneous, will always be classified as serious, recorded on an SAE CRF page, and expeditiously reported to the sponsor. Similarly, any congenital anomaly/birth defect in a child born to a female subject exposed to the investigational product will be recorded and reported as an SAE.

#### 8.3 Expedited Reporting Requirements for Serious Adverse Events

Any life-threatening (i.e., imminent risk of death) or fatal AE that is attributed by the investigator to the investigational product will be **telephoned to the Medical Monitor (or alternate) immediately**.

Medical Monitor:[name], PhDOffice [contact], ext. 7214Mobile [contact]

For initial SAE reports, investigators will record all case details that can be gathered within 24 hours on an SAE CRF page. The completed SAE CRF page will be faxed immediately upon completion to the attention of xxx

Relevant follow-up information will be submitted as soon as it becomes available and/or upon request.

#### 8.4 Type and Duration of Follow-Up of Subjects After Adverse Events

The Investigator will follow all unresolved study-emergent AEs and SAEs until the events are resolved, stabilized, the subject is lost to follow-up, or until it has been determined that the study treatment or participation is not the cause of the AE/SAE. Resolution of AEs and SAEs (with dates) will be documented on the appropriate AE or SAE CRF page and in the subject's medical record to facilitate source data verification. For some SAEs, the sponsor or its designee may follow-up by telephone, fax, electronic mail, and/or a monitoring visit to obtain additional case details deemed necessary to appropriately evaluate the SAE report (e.g., hospital discharge summary, consultant report, or autopsy report).

